6.2.6. Endpoints for immunogenicity data of avelumab

All analyses described below are performed by treatment arm containing avelumab (Arm A and Arm B), and for the avelumab-containing treatment arms combined unless otherwise specified.

Blood samples for avelumab immunogenicity testing will be collected within 2 hours before the start of the avelumab infusion on Day 1 of Cycles 1 through 4. Thereafter, a sample will be collected on Day 1 prior to avelumab infusion in Cycles 5, 6, 9, 12, 15, 18, 21 24 and at the End of Treatment. An additional sample must be collected at 30 days after the last dose of avelumab.

Samples positive for ADA will be analyzed for titer and may be analyzed for nAb. As of the finalization of this SAP, the nAb assay is not yet available, therefore the analyses of nAb data described in the following sections will only be conducted contingent upon assay and data availability at the time of reporting.

Patients will be characterized into different ADA categories based on the criteria defined in [Table 13](#).

Table 13 Patients Characterized Based on Anti-Drug Antibody Results (ADA Status)

Category	Definition	Subjects at Risk (Denominator for Incidence)
ADA never-positive	No positive ADA results at any time point; ADA-negative patients (titer < cutpoint)	Number of patients with at least one valid ADA result at any time point
ADA ever-positive	At least one positive ADA result at any time point; ADA-positive patients (titer ≥ cutpoint)	Number of patients with at least one valid ADA result at any time point
Baseline ADA positive	A positive ADA result at baseline	Number of patients with valid baseline ADA result
Treatment-boosted ADA	A positive ADA result at baseline and the titer ≥ 8×baseline titer at least once after treatment with avelumab	Number of patients with valid baseline ADA results and at least one valid post-baseline ADA result
Treatment-induced ADA	Patient is ADA-negative at baseline and has at least one positive post-baseline ADA result; or if patient does not have a baseline sample, the patient has at least one positive past-baseline ADA result	Number of patients with at least one valid post-baseline ADA result and without positive baseline ADA result (including missing, NR)

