Transient ADA response	If patients with treatment-induced ADA have (a single positive ADA result or duration between first and last positive result <16 weeks) and ADA result at the last assessment is not positive.	Number of patients with at least one valid post-baseline ADA result and without positive baseline ADA result (including missing, NR)
Persistent ADA response	If patients with treatment-induced ADA have duration between first and last positive ADA result ≥16 weeks or a positive ADA result at the last assessment	Number of patients with at least one valid post-baseline ADA result and without positive baseline ADA result (including missing, NR)

ADA: anti-drug antibody, NR = not reportable.

Patients will be characterized into different nAb categories based on the criteria in [Table 14](#). For nAb, treatment-boosted is not applicable since no titer result is available.

Table 14 Patients Characterized Based on Neutralizing Antibody Results (nAb Status)

Category	Definition	Subjects at Risk (Denominator for Incidence)
nAb never-positive	No positive nAb results at any time point	Number of patients with at least one valid ADA result at any time point
nAb ever-positive	At least one positive nAb result at any time point	Number of patients with at least one valid ADA result at any time point
Baseline nAb positive	A positive nAb result at baseline	Number of patients with valid baseline ADA result
Treatment-induced nAb	Patient is not nAb positive at baseline and has at least one positive post-baseline nAb result; or if patient does not have a baseline sample, the patient has at least one positive post-baseline ADA result	Number of patients with at least one valid post-baseline ADA result and without positive baseline nAb result (including missing, NR)
Transient nAb response	If patients with treatment-induced nAb have (a single positive nAb result or duration between first and last positive result <16 weeks) and nAb result at the last assessment is not positive.	Number of patients with at least one ADA valid post-baseline result and without positive baseline nAb result (including missing, NR)
Persistent nAb response	If patients with treatment-induced nAb have duration between first and last positive nAb result ≥16 weeks or a positive nAb result at the last assessment	Number of patients with at least one valid post-baseline ADA result and without positive baseline nAb result (including missing, NR)

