6.2.6.1. Time to and Duration of ADA and nAb response

The ADA and nAb analyses described below will include patients with treatment-induced ADA or nAb, respectively.

Time (weeks) to ADA response is defined as:

$$(\text{Date of first positive ADA result} - \text{date of first dose of avelumab} + 1)/7.$$

Time to ADA response will be summarized using simple descriptive statistics (mean, SD, median, min, max, Q1, Q3).

Duration (weeks) of ADA response is defined as:

$$(\text{Date of last positive ADA result} - \text{date of first positive ADA result} + 1)/7.$$

Duration of ADA response will be censored if:

- the last ADA assessment is positive AND patient is ongoing treatment with avelumab, or

- the last ADA assessment is positive AND patient discontinued treatment with avelumab AND the last planned ADA assessment (30 days after the last dose of avelumab) is after the cut-off date.

Time to nAb response and duration of nAb response are defined similarly based on first and last positive nAb result.

Kaplan-Meier estimates (product-limit estimates) will be presented together with a summary of associated statistics including the median ADA response time with 2-sided 95% CIs. ADA response rates at different timepoints will be estimated with corresponding 2-sided 95% CIs. The CIs for the median will be calculated according to Brookmeyer and Crowley (1982) and the CIs for the survival function estimates will be derived using the log-log transformation according to Kalbfleisch and Prentice (2011) (confotype=loglog default option in SAS Proc LIFETEST) with back transformation to a CI on the untransformed scale. The estimate of the standard error will be computed using Greenwood's formula.

Duration of ADA response will be displayed graphically and analyzed using Kaplan-Meier methodology. If the number of patients with ADA response is small, the Kaplan-Meier method may not provide reliable estimates. In this case, only descriptive statistics or listings will be provided

As data permit, the analyses described above will be repeated for patients with treatment-induced nAb.

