6.2.6.3. Analysis of PK, safety and efficacy by immunogenicity status

The following ADA and nAb status will be used for the analyses described below.

ADA

- ADA ever-positive versus ADA never-positive
- ADA: treatment-induced ADA versus ADA never-positive or baseline ADA positive

nAb

- nAb ever-positive versus nAb never-positive
- nAb: treatment-induced nAb versus nAb never-positive or baseline nAb positive

Data listings will include immunogenicity data together with relevant PK, safety and efficacy data.

PK parameters and immunogenicity status

The following analyses will include patients in both the immunogenicity analysis set and in the PK parameter analysis set. The PK endpoints pertinent to the immunogenicity analyses are C_{trough} and C_{max} .

Blood samples for avelumab PK will be collected pre-dose and at the end of infusion (immediately before the end of avelumab infusion) on Days 1 and 15 of Cycles 1 to 4. Pre-dose samples should be collected on Days 1 of Cycles 5, 6, 9, 12, 15, 18, 21 24; at the End of Treatment and at Day 30 Safety Follow-up visit.

C_{trough} and C_{max} will be summarized descriptively (n, mean, SD, CV, median, minimum, maximum, geometric mean, its associated CV, and 95% CI) by nominal time and ADA status. Linear-linear and log-linear plots of mean and median for C_{trough} and C_{max} over nominal time and by ADA status will be presented.

Among patients with treatment-induced ADA, analyses will be conducted to assess whether C_{trough} and C_{max} have any changes before and after the first positive ADA assessment. To be included in this analysis, patients must have the same PK parameter available both before and after the first positive ADA assessment. Relative PK day will be calculated as:

$$(\text{PK assessment nominal day}) - (\text{first positive ADA assessment nominal day}).$$

Nominal day is the protocol scheduled timing for an assessment. For example, if C_{trough} is collected on Day 1 of Cycle 2 and the first positive ADA result is observed on Day 1 of Cycle 3, then the relative PK day for this C_{trough} is -28. Linear-linear and log-linear plots of mean and median for C_{trough} and C_{max} over relative PK day will be presented.

As data permit, the analyses described above will be repeated for nAb.

Safety and immunogenicity status

The following analyses will include patients in the immunogenicity analysis set.

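### SAP Table 14 classes a patient with no baseline sample as treatment-induced nAb on a positive ADA result alone, so a patient with no positive nAb result can fall on both sides of one nAb comparison

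*SAP*

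**What the plan says.** SAP Section 6.2.6 sorts patients by ADA status in Table 13 and by nAb status in Table 14. The entries that matter are these.

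- **Table 14, treatment-induced nAb, first limb:** "Patient is not nAb positive at baseline and has at least one positive post-baseline nAb result".
- **Table 14, treatment-induced nAb, second limb, for a missing baseline sample:** "if patient does not have a baseline sample, the patient has at least one positive post-baseline ADA result".
- **Table 14, nAb never-positive:** "No positive nAb results at any time point".
- **Table 13, treatment-induced ADA, the matching limb:** "if patient does not have a baseline sample, the patient has at least one positive past-baseline ADA result".

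On testing, the same section states: "Samples positive for ADA will be analyzed for titer and may be analyzed for nAb". It also says that, when the SAP was finalized, "the nAb assay is not yet available", and it makes all nAb analyses conditional on the assay and data being available at reporting.

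Section 6.2.6.3 sets two nAb groupings for the PK and safety summaries. One is ever-positive against never-positive. The other is "nAb: treatment-induced nAb versus nAb never-positive or baseline nAb positive".

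Section 6.2.6.1 restricts the time-to-response and duration analyses to treatment-induced patients and adds: "Time to nAb response and duration of nAb response are defined similarly based on first and last positive nAb result".

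**The concern.** Table 14 is built as the nAb counterpart of Table 13, and every other category definition in it rests on nAb results. In the missing-baseline limb the deciding result is ADA. A positive ADA result does not make a patient nAb-positive, and because nAb testing of ADA-positive samples is optional, it does not even show that nAb was tested.

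A programmer who follows the table would count some patients with no positive nAb result as treatment-induced nAb. Those patients also satisfy the never-positive definition in the same table. The treatment-induced count would be too high, and one of the two nAb groupings would no longer have mutually exclusive groups. Neither document corrects the clause or says which category takes precedence.

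**Working it through.** The plan gives no figure to reproduce, so the check is a complete listing of cases.

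**Inputs.** There are four baseline states: no sample; ADA-negative; ADA-positive without a positive nAb result; ADA-positive and nAb-positive. There are three post-baseline states: ADA-negative; ADA-positive without a positive nAb result; ADA-positive and nAb-positive. This gives 4 × 3 = 12 patient types. A sample that was not tested for nAb counts as having no positive nAb result. Following Section 6.2.6, nAb is considered only in ADA-positive samples.

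**Rules applied.** TI is treatment-induced nAb under Table 14 as written. The comparator is nAb never-positive or baseline nAb positive, from Section 6.2.6.3.

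| Baseline | Post-baseline | TI as written | Comparator | In both |
|---|---|---|---|---|
| No sample | ADA− | no | yes | |
| No sample | ADA+, no nAb+ | **yes** | **yes** | **yes** |
| No sample | ADA+, nAb+ | yes | no | |
| ADA− | ADA− | no | yes | |
| ADA− | ADA+, no nAb+ | no | yes | |
| ADA− | ADA+, nAb+ | yes | no | |
| ADA+, no nAb+ | ADA− | no | yes | |
| ADA+, no nAb+ | ADA+, no nAb+ | no | yes | |
| ADA+, no nAb+ | ADA+, nAb+ | yes | no | |
| ADA+, nAb+ | ADA− | no | yes | |
| ADA+, nAb+ | ADA+, no nAb+ | no | yes | |
| ADA+, nAb+ | ADA+, nAb+ | no | yes | |

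**Result.** As written, 1 of 12 types falls in both groups and the other 11 fall in exactly one. With nAb in place of ADA in the missing-baseline limb, 0 of 12 fall in both and 0 of 12 in neither, so the two groups partition the patients.

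**Consequences for that one type.**

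1. *Treatment-induced row of Table 14.* The denominator admits patients with a missing baseline, so it is the same under either wording. The numerator gains the patient wrongly, and the percentage rises.
2. *Second nAb grouping in Section 6.2.6.3.* The patient contributes to both columns of the PK and safety summaries by status.
3. *Time to and duration of nAb response, Section 6.2.6.1.* The patient belongs to the analysis set but has no positive nAb date, so neither quantity can be calculated.
4. *Transient and persistent rows.* Each needs at least one positive nAb result, so the patient meets neither. The two rows keep their own counts but no longer add up to the treatment-induced row.

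**How many patients.** The count would be the number of avelumab patients × the share with no baseline sample × the share of those ADA-positive afterwards × the share of those with no positive nAb result. The planned design puts about 550 × 2/3 ≈ 367 randomized patients in the two avelumab arms. The documents give none of the three shares, so the product cannot be evaluated. The only lower limit is zero.

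**The case against.** The strongest reply is that the clause may never be executed, and that it reaches little if it is. Much of that stands.

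- **The analyses are conditional.** With no assay at SAP finalization, the nAb tables may not be produced. This limits the practical weight of the point but does not make the definition right.
- **Baseline samples should rarely be missing.** Sampling is scheduled before the first infusion on Cycle 1 Day 1. Even so, the SAP provides for the gap: Table 14 keeps patients with a missing baseline in its denominators, and Section 4.3.4 admits a patient to the immunogenicity set with a single sample.
- **The transient and persistent results might seem distorted.** A reader might infer this because both categories are subsets of treatment-induced nAb. The documents do not support it: both rows require a positive nAb result and carry their own denominators, so neither changes.
- **The time-to-response and duration estimates might seem biased.** Section 5.3.1 rules out imputation unless specified. A patient with no positive nAb date would have a missing value and contribute no time. The effect is a mismatch in counts, not a shifted estimate.
- **A named secondary endpoint might seem wrong.** Protocol Section 2.2 lists nAb incidence, and Protocol Section 9.3.2 describes it as the percentage of patients with positive neutralizing antibodies. That corresponds to the ever-positive row, which the clause does not touch.

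One defence fails. The ADA wording might be meant to catch nAb cases that would otherwise be lost when the baseline is missing. But nAb is tested only in ADA-positive samples, so a patient with no baseline sample and a positive post-baseline nAb result is captured under either wording. The only net effect of the ADA wording is to add patients who have no positive nAb result. The ADA-based denominators in Table 14 do not rescue it either: they define who is at risk, not who is a case.

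**Conclusion.** The point holds as a narrow definitional error, on the plain wording of Table 14 and provided that the nAb analyses are run. It overstates the treatment-induced nAb row, makes the groups overlap in one of the two nAb groupings used for PK and safety by status, and leaves the time-to-response and duration set with patients who have no usable date.

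It goes no further. The ever-positive versus never-positive grouping stays mutually exclusive. The overall nAb-positive incidence and all ADA analyses are unchanged, and the efficacy listing and plot in Section 6.2.6.3 select on ADA ever-positive status. OS and PFS are untouched. A reader might want to attach a number of misclassified patients by assuming rates for missing baselines and ADA positivity. The documents anchor no such rates, and a product that leaves out the share with no positive nAb result would be only an upper bound. The number may be zero.

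That the clause was copied from Table 13 is an inference from the near-identical wording; the conclusion does not depend on it.

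**What to change.** In SAP Table 14, in the missing-baseline limb of treatment-induced nAb, replace ADA with nAb so that the limb requires at least one positive post-baseline nAb result. No other row, denominator or comparison needs to change: the two groups in Section 6.2.6.3 then separate cleanly, and the transient and persistent rows again add up to the treatment-induced row.

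The cost is one word in the SAP and the matching line in the derivation program. No design element, sample or data collection is affected. If the correction is made before nAb results are examined, it cannot be seen as driven by them. If nAb outputs already exist, check the treatment-induced group for patients with no positive nAb date, and rerun the affected summaries if there are any.

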6.2.6.1. Time to and Duration of ADA and nAb response

The ADA and nAb analyses described below will include patients with treatment-induced ADA or nAb, respectively.

Time (weeks) to ADA response is defined as:

$$(\text{Date of first positive ADA result} - \text{date of first dose of avelumab} + 1)/7.$$

Time to ADA response will be summarized using simple descriptive statistics (mean, SD, median, min, max, Q1, Q3).

Duration (weeks) of ADA response is defined as:

$$(\text{Date of last positive ADA result} - \text{date of first positive ADA result} + 1)/7.$$

Duration of ADA response will be censored if:

- the last ADA assessment is positive AND patient is ongoing treatment with avelumab, or

- the last ADA assessment is positive AND patient discontinued treatment with avelumab AND the last planned ADA assessment (30 days after the last dose of avelumab) is after the cut-off date.

Time to nAb response and duration of nAb response are defined similarly based on first and last positive nAb result.

Kaplan-Meier estimates (product-limit estimates) will be presented together with a summary of associated statistics including the median ADA response time with 2-sided 95% CIs. ADA response rates at different timepoints will be estimated with corresponding 2-sided 95% CIs. The CIs for the median will be calculated according to Brookmeyer and Crowley (1982) and the CIs for the survival function estimates will be derived using the log-log transformation according to Kalbfleisch and Prentice (2011) (confotype=loglog default option in SAS Proc LIFETEST) with back transformation to a CI on the untransformed scale. The estimate of the standard error will be computed using Greenwood's formula.

Duration of ADA response will be displayed graphically and analyzed using Kaplan-Meier methodology. If the number of patients with ADA response is small, the Kaplan-Meier method may not provide reliable estimates. In this case, only descriptive statistics or listings will be provided

As data permit, the analyses described above will be repeated for patients with treatment-induced nAb.

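### ADA duration: patients off avelumab who are still ADA-positive at their last sample count as Kaplan-Meier events if the 30-day sample was due by the cut-off

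*SAP*

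**What the plan says.** SAP Section 6.2.6.1 sets the population: "The ADA and nAb analyses described below will include patients with treatment-induced ADA or nAb, respectively". Duration in weeks runs from the first positive sample to the "Date of last positive ADA result", plus one day, divided by 7. No negative sample is needed to close the interval.

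There are two censoring conditions, and both require a positive last result. The first reads "the last ADA assessment is positive AND patient is ongoing treatment with avelumab, or". The second applies once avelumab has been stopped, "AND the last planned ADA assessment (30 days after the last dose of avelumab) is after the cut-off date". The method is then fixed: "Duration of ADA response will be displayed graphically and analyzed using Kaplan-Meier methodology". The rule carries over to neutralizing antibodies: "Time to nAb response and duration of nAb response are defined similarly based on first and last positive nAb result".

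SAP Section 6.2.6 plans no ADA sample later than the one 30 days after the last dose. In Table 13 of that section, a persistent response is a treatment-induced ADA with "duration between first and last positive ADA result ≥16 weeks or a positive ADA result at the last assessment". A transient response requires that the last result is not positive. Table 14 uses the same structure for nAb.

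**The concern.** In a Kaplan-Meier analysis of response duration, an event should mean that the response was seen to end. Here one group becomes an event on a day when antibody was measured as present: patients off avelumab, last result positive, 30-day sample due on or before the cut-off. It includes patients positive at the 30-day sample itself. It also includes patients who were positive earlier and then died, withdrew or missed that sample.

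The SAP handles its other durations differently. Duration of tumour response (Section 6.2.2.5) and time to deterioration (Section 6.2.7.4) are censored when no event was observed. Section 6.2.6.2 switches censoring off only for the cross-tabulation of duration against titre, which implies that the Kaplan-Meier analysis is meant to respect it.

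At stake is what the reported median and the ADA response rates over time mean. For this group they record when sampling stopped, not when antibody cleared. Immunogenicity of avelumab is a stated secondary objective.

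**Working it through.** The SAP gives no figure for ADA duration, so there is none to reproduce. The check has three parts.

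**1. Enumerating the rule for a positive last result**

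- Still on avelumab: censored.
- Off avelumab, 30-day date after the cut-off: censored.
- Off avelumab, 30-day date on or before the cut-off: event.

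Extreme case: the only positive is the 30-day sample. Duration = (0 + 1)/7 = 0.14 weeks, uncensored, and the patient is persistent under Table 13.

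*Direction.* Relabelling a censored time as an event at the same time can only lower the Kaplan-Meier curve or leave it unchanged, so the bias is always towards shorter duration.

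**2. Share of patients still in a censoring branch at the final cut-off**

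Inputs from SAP Section 5.1.1: accrual over 19 months, at least 12 months of follow-up after the last randomization (so 12 to 31 months), and a planned median PFS of 5.8 months in the avelumab arms. Assumptions: time on avelumab is exponential with that median, and accrual is uniform (the SAP says non-uniform).

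- k = ln 2/5.8 = 0.1195 per month.
- Still on avelumab: [exp(−12k) − exp(−31k)]/(19k) = (0.2383 − 0.0246)/2.2707 = 0.094.
- On avelumab or less than 30 days off it: multiply by exp(k × 30/30.4375) = 1.125, giving 0.106.

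So about 9% are on avelumab and about 11% are in either branch. Accrual shape does not rescue the rule. If every patient had only 12 months of follow-up the share would be exp[−k(12 − 0.986)] = 0.27; at 31 months it would be 0.03.

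**3. Illustrative simulation**

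Each scenario used 20,000 patients on the SAP's ADA visit schedule, with time on avelumab and accrual as above. Further assumptions, none in the documents: exponential time to ADA onset (median 8 weeks), exponential true ADA duration, and an End of Treatment sample 14 days after the last dose. Medians are in weeks.

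| True median | Last result positive | Of these, counted as events | False events, share of all treatment-induced ADA | KM median, rule as written | KM median, corrected rule |
|---|---|---|---|---|---|
| 8 | 29% | 98.5% | 29% | 4.1 | 8.1 |
| 16 | 42% | 97.0% | 41% | 8.1 | 12.1 |
| 26 | 56% | 94.0% | 53% | 10.4 | 24.1 |
| 52 | 71% | 91.3% | 65% | 14.4 | 58.1 |
| Never lost | 100% | 87.5% | 87.5% | 22.4 | not reached |

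The fourth column is the product of the second and third. It separates false events from patients whose last result was not positive and who are properly events. In the last row, where no response ever ends, the written rule still reports a median of 22.4 weeks and puts the proportion still positive at 16 weeks at 0.62 instead of 1.00.

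**The case against.** The best defence is that little depends on this output. The protocol's immunogenicity endpoint is the incidence of ADA and nAb (Section 2.2), and Section 9.3.2 promises only a description of duration where data allow. Duration has no test, alpha or decision rule. SAP Section 6.2.6.3 lists first and last positive dates and duration for every ADA ever-positive patient, and the persistent count keeps still-positive patients visible. Section 6.2.6.1 drops Kaplan-Meier if responders are few. Neither document gives an expected ADA rate, so the curve may never be produced. The nAb assay was not available when the SAP was finalized. All of this stands and limits the consequence, but none of it corrects the censoring rule.

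A reader might infer that Table 13 and Section 6.2.6.1 contradict each other. The documents do not support that. The second limb of the persistent definition admits a patient on a positive last result whatever the measured span, so a short span in a persistent patient is allowed by definition. The fault is that an observed span is treated as a completed one.

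The proxy is also open to challenge. PFS is not time on avelumab; Protocol Section 3.1.2 shows that some patients stayed on avelumab after progression. The 3.5-month PFS median must not be used here, because it belongs to the PLD control arm and ADA is analysed only in Arms A and B.

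Last, the corrected rule is not unbiased: in the table it gives 12.1 for a truth of 16 and 58.1 for 52. Patients who turn negative still have their event placed at the last positive sample, across 12-week gaps after Cycle 6. That shortening is a separate matter and remains.

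**Conclusion.** The point holds for a defined group: treatment-induced ADA patients off avelumab, last result positive, planned 30-day sample date on or before the cut-off. They enter Kaplan-Meier as events with no negative result observed. A reader might infer that every last-positive patient is treated this way, but two such groups are censored. On the planned figures those two branches would hold only about 9% to 11% of patients at the final cut-off, so most last-positive patients would be false events.

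The downward direction follows from the rule alone. The 9% to 11% rests on the 5.8-month PFS proxy, exponential times and uniform accrual. The simulated medians rest on further assumed onset and duration inputs; they illustrate the mechanism and do not estimate this trial's bias.

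A reader might also infer that the trial's immunogenicity finding or its efficacy conclusions are affected. They are not: ADA and nAb incidence, the persistent and transient counts, OS and PFS are untouched. The damage is confined to the descriptive ADA duration output and, if the assay is available, its nAb counterpart. Within that limit the rule should be corrected.

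**What to change.** Replace the two censoring conditions in SAP Section 6.2.6.1 with one: censor duration at the last positive date whenever the patient's last valid ADA result is positive, whatever the treatment status or cut-off. Count an event only when a later valid result is negative. Apply the same rule to nAb.

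This costs one SAP sentence and one programming condition. It needs no new samples, so it can be re-run on existing data even though the final analysis is complete (Protocol Section 9) and ADA sampling has stopped (Protocol Section 7.3.2). There will be fewer events, so the median may not be reached. The interval-sampling error described above remains and deserves a footnote to the output.
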